Participants will attend eight 90-minute group treatment sessions scheduled on average twice per week for four weeks. In all three treatment conditions, group sessions will be conducted via the online, HIPAA-compliant Zoom videoconferencing platform (<https://zoom.us/>) with support from UW IT Services. Zoom videoconferences allow participants to see and hear each other, and also allows screen sharing, giving clinicians the opportunity to display visual information (e.g., PowerPoint slides) during the session. In the event that a participant cannot access the videoconference during a specific session, we will provide workbooks to follow along with and to facilitate skills practice outside of sessions.

Participants may participate in Zoom sessions through a smart phone, tablet, laptop, or desktop computer. All participants will be provided instructions and training prior to their first scheduled session on how to log in, join the session, set up their video/audio components, and how to navigate the various menus/buttons within Zoom. Finally, participants are required to participate in sessions in a quiet, private location free from distractions to maximize treatment

engagement and to protect the privacy and confidentiality of the sessions (e.g., their home or private office).

The group sessions will be conducted by PhD- or Masters-level clinicians with at least two years of clinical experience and who have undergone training that prepares clinicians to conduct each of the three treatment interventions in a group setting. The study clinicians will be trained and supervised by the investigators who have a great deal of experience in providing the study treatments. The clinicians will be provided with a detailed treatment manual and protocol outline, and Drs. [name] (CT intervention), [name] (MM intervention), or [name] (AS intervention) will provide regularly scheduled (weekly for the first two cohorts facilitated by any new study clinician; this may decrease to twice monthly once the study clinician has experience with the interventions and has demonstrated at least 90% treatment fidelity for the interventions provided) supervision for the study clinicians.

We will have a goal of having each group led by one or two clinicians allowing for groups to continue as scheduled in the event one of the clinicians is unable to attend a particular group.

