- (3) If less than small effects emerge for both the between-group effects on the early mechanism slope *and* for the time effect (i.e., average slope), this would be interpreted to indicate a lack of early change (in any treatment condition) on the mechanism variable. In this instance, that mechanism variable would not be tested in a subsequent SEM. If *either* of the effect sizes are equal to or larger than 0.01 (indicating a small or larger time effect, on average) or a small or large Group X Time effect emerges (indicating at least a small group effect on early change in mechanism), then we will proceed to Step 2 for that mechanism variable.

Step 2. Test the model presented in Figure 3 for any mechanism variable that met the Step 1 conditions described above.

- (4) First paths a_1 and a_2 will be tested. The a_1 and a_2 coefficients represent the strength of the predictive relationships from the two dummy IVs¹ to early treatment slope in catastrophizing (i.e., to evaluate the impact of treatment condition on early treatment changes in catastrophizing). Together, these tell us if treatment condition had a direct effect on the early treatment slope in the mechanism variables. If both of these coefficients are non-significant (consistent with the Shared Mechanisms Model) they will be eliminated from the final SEM. If either or both of these pathways are statistically significant, this will be interpreted to mean that there is a between-treatment condition difference in early change in the mechanism variable being evaluated, and these effects will be retained in the model.
- (5) In the case of at least one statistically significant a coefficient, we will perform planned post-hoc ANOVA models for each of the three treatment groups to understand these differences and to determine if the findings are consistent with the Specific Mechanisms Model. For example, if catastrophizing is uniquely targeted by CT, we would anticipate a significant treatment condition effect (in either or both of the two a coefficients) on early catastrophizing slope, with post hoc tests indicating larger pre- to mid-treatment decreases in catastrophizing for the CT condition than the MM or AS interventions. However, the full test of the Specific Mechanisms Model also takes into account the b path, described below.

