¹ In the proposed SEM, treatment condition (i.e., which of three treatments the participant is assigned to) is represented by two variables: "CTvsOther" (coded as "1" if the participant is assigned to the CT condition, "0" if not) and "MMvsOther" (coded as "1" if the participant is assigned to the MM condition, "0" if not). These two dummy variables are exogenous and have a correlation of $r = .50$ (if groups are of equal size). When considered in the same model (i.e., when controlling for the other), the two variables contain information about all three treatment conditions.

[figure not shown]
(6) In order to establish a mechanism effect on outcome (i.e., that cognitive content, cognitive process, or activity level predicts subsequent change in pain interference) we will next test for significance of the *b* coefficients. We will test the *b* coefficient for significance across each of the three mechanism variables (i.e., three significance tests, one per SEM model). Any *b* coefficients that are not significant indicate that early change in that mechanism variable is not associated with late change in pain interference, indicating a lack of support for it as a mechanism variable in treatment. A significant *b* coefficient will be interpreted as evidence supporting early treatment change in the mechanism variable in question as explaining late treatment change in pain interference.

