As indicated, up to three SEMs (one for each mechanism) will evaluate and test for significance of the *a* and *b* coefficients for each mechanism variable that met the Step 1 assumptions described above (i.e., that evidenced at least a small early slope or larger, for at least one of the treatments). The combination of a treatment effect on the mechanism variable (coefficient *a*) and a significant *b* coefficient for a particular mechanism variable (indicating that early change in the mechanism variable predicts a late change in outcome), with *post hoc* tests linking each treatment to its targeted mechanism variable (i.e., CT, MM, and AS having the largest effects on cognitive content, cognitive process, and activity level, respectively) would support the Specific Mechanisms Model. A significant *b* coefficient in light of non-significant *a* coefficients (i.e., the mechanism plays a role in outcome, but all three treatments have a similar impact on the mechanism variable) would support a Shared Mechanisms Model. Thus, together, the significance levels of the *a* and *b* coefficients will address the study aims. In short, the results of the (maximum) six planned statistical tests (i.e., whether or not there are between-group differences in the three early mechanism slopes, and the significance level of the three *b* coefficients) will allow us to evaluate if the three mechanism variables play a role in treatment outcome, and whether this role is shared between the treatments or unique to a subset of them.

Exploratory Moderation Analyses

We also plan to conduct a preliminary test of the LAE model. Specifically, SEM will be used to evaluate the extent to which baseline catastrophizing, activity levels, and non-judgment are respectively associated with response to CT, AS, and MM. Figure 4 below illustrates the statistical approach that we propose to use to evaluate the LAE model. For illustrative purposes, only the role of baseline catastrophizing moderating response to treatment is depicted. As per the above models, the treatment condition variable is represented by two variables: "CTvsOther" (coded as "1" if the participant is assigned to the CT condition, "0" if not) and "MMvsOther" (coded as "1" if the participant is assigned to the MM condition, "0" if not). When considered in the same model (i.e., when controlling for the other), the two variables contain information about all three treatment conditions.

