Assuming at least medium effects (i.e., $rs \geq .30$ and/or $ds \geq .50$), we can then compute the sample sizes needed to detect significant effects for the planned primary analyses, using the Hochberg and Benjamini procedure to control for alpha inflation in these analyses. This alpha control procedure involves putting the significance levels of the six planned primary analyses in ascending order, and matching them to the actual significance levels obtained with the six analyses, also placed in ascending order. The number needed to detect significant effects for each of these analyses is presented in Table 5, below, using the tests for the three direct mediation effects of the mechanism variables for three of these analyses, and a test for the three Treatment Condition X Mediation (representing moderated mediation) effects for the other three analyses, assuming at least medium effects for each of these effects. Sample size estimates needed to detect the primary mediation effects were conducted based on the joint significance method of testing mediated effects, using the PowMedR program in R Version 3.0.2 statistical software with the following assumptions: (1) alpha levels consistent with the Hochberg and Benjamini procedure (see Table 5, below); (2) power of 0.80; and (3) at least medium effects. Power calculations for the interaction (mediated moderation) analyses were conducted using G*Power3 with the same assumptions.

Table 5. Sample size estimates for the six planned analyses, assuming medium effects for the causal paths (a and b) and at least a medium interaction effect (f^2) for the three planned Treatment Condition X Mediation effects tests

Alpha	Power	Effect size path a	Effect size path b	Interaction effects	n-required / n-planned
0.050	0.80	Medium ($r = 0.30$)	Medium ($r = 0.30$)		109 / 240
0.025	0.80	Medium ($r = 0.30$)	Medium ($r = 0.30$)		129 / 240
0.017	0.80	Medium ($r = 0.30$)	Medium ($r = 0.30$)		140 / 240
0.013	0.80			Medium ($f^2 = 0.15$)	93 / 240
0.010	0.80			Medium ($f^2 = 0.15$)	98 / 240
0.008	0.80			Medium ($f^2 = 0.15$)	102 / 240

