Previous studies with the therapeutic skills taught in the planned study support their efficacy in reducing pain interference and improving other pain-related outcomes. We anticipate based on this previous research that many of the participants will experience significant reductions in their daily pain interference and other benefits associated with the treatments. Participants in all three conditions will have the benefit of a caring and interested group leader, thus promoting therapeutic alliance, as well as interaction with other group members.

In our past research, many group members have expressed satisfaction from learning that there are other people with experiences similar to their own, and from receiving group treatment in a caring and nonjudgmental environment. Thus, participants in all three treatments will take away from the study new skills and knowledge regarding chronic pain and how to manage it, and – given previous results of RCTs for psychosocial interventions for chronic pain – should experience some degree of relief from pain and suffering and increases in their quality of life.

H. Publication of Research Findings

Any manuscript will be made available for review by the study sponsor prior to submission.

I. Importance of Knowledge to Be Gained

The findings from this study will provide clinically meaningful information that will have positive effects on the lives of patients with chronic pain who endorse low back pain as a primary or secondary pain problem. The findings will provide important new information regarding mechanisms of the treatments studied, as well as those factors that underlie post-treatment relapse, maintenance, and continued gains following treatment. Results will elucidate the temporal sequence of lagged mechanism effects to determine rates of change in outcome as a function of change in cognitive content, cognitive process, and behavioral activity level. Results will also precisely inform relapse prevention interventions. As pointed out by Kazdin,^{12,13} progress in our understanding of treatments has been hampered by the lack of mechanism studies, such as the one planned, to identify the mechanisms of treatment outcome and relapse. The current study will help address this significant gap. The exploratory moderation findings will inform the future development of patient-treatment matching algorithms.

References

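### The between-treatment gate tests two coefficients per mechanism where the plan budgets one test, and it treats members of the same treatment group as independent

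*Combined protocol and SAP*

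**What the plan says.** In D6s, Step 2, treatment enters each mechanism model as two dummies, CT against the rest and MM against the rest, with AS as reference. The footnote explains that, taken in one model, "the two variables contain information about all three treatment conditions". Item (4) then gives the rule. For Shared: "If both of these coefficients are non-significant (consistent with the Shared Mechanisms Model) they will be eliminated from the final SEM". For a difference: "If either or both of these pathways are statistically significant, this will be interpreted to mean that there is a between-treatment condition difference". Item (5) repeats the at-least-one condition as the trigger for the follow-up: "we will perform planned post-hoc ANOVA models for each of the three treatment groups". Its worked example compares CT with both MM and AS.

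The paragraph after item (6) counts differently: "the results of the (maximum) six planned statistical tests (i.e., whether or not there are between-group differences in the three early mechanism slopes", plus the three b coefficients. D6u also counts six: "This alpha control procedure involves putting the significance levels of the six planned primary analyses in ascending order". There, however, the three treatment-related tests are Treatment Condition by Mediation interactions, not a1 and a2.

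On delivery, D6m says: "In all three treatment conditions, group sessions will be conducted via the online, HIPAA-compliant Zoom videoconferencing platform". Section G lists among the expected benefits of all three conditions a caring leader "as well as interaction with other group members", and Table 3 makes group cohesion a secondary mechanism. D6s, D6t and D6u name no group term, ICC or design effect. The only standard-error correction described, in D6t, is for non-normality. Figure 3 is not visible in the text, but its description contains no group level.

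**The concern.** The a-result decides whether a mechanism is labelled Shared or can go forward as Specific, and it supplies three of the six primary tests. Two features make it too easy to declare a difference.

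First, each mechanism gets two chances to be significant while the multiplicity plan charges for one. The pair consists of CT against AS and MM against AS. CT against MM is not part of the gate and is reached only in the post hoc step, which runs only after a significant a.

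Second, if members of a treatment group change together, arm means vary more than an analysis of independent participants allows, and the a-path p-values are too small. Both features push away from Shared. The b paths, estimated from differences between individuals, are little affected.

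**Working it through.** **The plan's own figure.** Table 5's interaction rows (f² = .15, power .80, alpha .013, .010 and .008) give 93, 98 and 102. A noncentral F with lambda = .15N and two numerator df reproduces all three exactly; one df gives 77, 82 and 85. So power was computed for a two-df treatment term, whereas item (4) decides on single coefficients.

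**Test count.** Item (4): 2 coefficients x 3 mechanisms + 3 b-tests = 9. Closing paragraph of the Step 2 text: 3 + 3 = 6.

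**Error of the either-or rule, independent data.** With equal arms and a shared reference, the estimates of a1 and a2 correlate +.50. (The dummies themselves correlate -.50; the footnote omits the sign.) The rate is 1 - P(|Z1| < c and |Z2| < c) at correlation .5:

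- .05 for each coefficient: 9.1%
- .05/6 = .0083 for each: 1.6%

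Table 5's alphas are .05/k, the Hochberg steps. Family-wise rate under the global null, by simulation:

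- smaller p of each pair in one of six slots: 7.1-7.2%
- nine p-values entered: about 4.8%
- one joint test per mechanism, six p-values: 5.0%

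**Power of the gate.** Inputs: 80 per arm, r = .30 (R² = .09), no clustering, alpha .05/6.

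| Pattern | Either-or | Joint two-df |
|---|---|---|
| CT or MM differs from the other two | 94.5% | 96.8% |
| AS differs from the other two | 98.5% | 96.8% |
| AS midway between CT and MM | 74% | 97% |

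Hypothesis 1c predicts the first two patterns, not the third.

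**Clustering.** D2 gives 3.5 years of enrolment and D6l gives 3-5 cohorts a year: 10.5 to 17.5 cohorts, taken as 11 and 18. One group per arm per cohort (an assumption) gives 33 or 54 groups. With 240 completers, mean size m is 240/33 = 7.27 or 240/54 = 4.44. The design effect is DE = 1 + (m - 1) x ICC. A joint two-df test at 5% that ignores groups has approximate size P(chi-square on 2 df > 5.99/DE) = .05^(1/DE).

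| ICC (assumed) | DE, 54 to 33 groups | Approximate size |
|---|---|---|
| .01 | 1.034 to 1.063 | 5.5 to 6.0% |
| .05 | 1.172 to 1.314 | 7.8 to 10.2% |
| .10 | 1.344 to 1.627 | 10.8 to 15.9% |

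Simulations on the same layout agree: about 5.4-6.0%, 8-10% and 11-16%. The either-or rule at .05 each, groups ignored, gives 13-15% at ICC .05 and 17-22% at .10.

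If half the clustering is cohort-wide, that half cancels between arms and DE = 1 + (m/2 - 1) x ICC. Size is then about 5.9-7.1% at ICC .05 and 6.9-9.3% at .10.

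**The case against.** **Test count.** Item (4) says that the two coefficients jointly convey whether treatment had an effect, and D6s applies its multiplicity procedure to all analyses. But no joint test follows, and item (5) again asks for at least one significant coefficient. The exploratory moderation section, by contrast, does combine c1 and c2 into one parameter. It is fair that 9.1% applies at .05 per coefficient, that the family-wise figure is nearer 7%, and that entering nine p-values would restore control without any new model.

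**CT against MM.** A reader might infer that this comparison is never made. The documents do not support that: item (5) has it post hoc. Nor do they support a large general loss of power, since under Hypothesis 1c the either-or rule is about 2 points worse or better than the joint test.

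**D6u.** One might read it as also budgeting a single a-test per mechanism. It supports the number six, but for a different hypothesis, so it and the closing D6s paragraph need reconciling.

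**Clustering.** The ICC is wholly assumed. The outcome is an individual 14-day slope that may rest on two ratings, so noise would dilute any group effect. E3b says personal disclosure is not specifically elicited. D6l has each clinician offer groups of every type, and cohorts contain all arms, so mainly the peer component matters. More and smaller groups would lower DE. All of this limits the size; none of it puts a group term in the analysis.

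**Covariates.** One might add that unadjusted minimization factors distort the a-tests. D6s tests covariates and controls for them when indicated. In simulation, keeping the three factors at p < .05 gave size 5.0, 4.6 and 5.0% when they explained 5, 10 and 20% of variance, the same as always including them. That is not a defect here.

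**Conclusion.** Both parts hold. The two-for-one rule contradicts the plan's own count and needs no outside assumption: 9.1% per mechanism at .05 each, or about 7% family-wise over six slots. The omission of treatment group is also real, but its effect depends on an ICC the documents do not give and on one group per arm per cohort. It is slight at .01 and material at .05 to .10, less if part of the clustering is cohort-wide.

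It would be wrong to read these rates as rates of false Specific conclusions. Specific also needs a significant b and the predicted post hoc order, and that combined rate has not been calculated. Nor should an effective sample size above 140, Table 5's largest requirement, be taken as reassurance: that row is a mediation test at alpha .017, not the arm test. The point should be settled before analysis but does not undermine the design.

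**What to change.** 1. In D6s item (4), replace the either-or rule with one joint two-df test of a1 and a2 per mechanism, as the moderation section already does for c1 and c2. Enter that single p-value in the six-test ordering, and let it decide whether the a-paths stay in the SEM and whether item (5) runs.
2. In that test and in the post hoc comparisons, including CT against MM, account for treatment group of assignment. Either a group random effect with small-sample degrees of freedom or an analysis of group means with cohort will do. In simulation, a group-means test with cohort had size 4.5-5.5%. Report a1 and a2 from the SEM as estimates.
3. Reconcile the closing D6s paragraph with D6u on which three treatment tests are primary.

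The cost is a few lines of SAP text, one further model per mechanism on data already held, wider intervals on arm contrasts, and some power. Simulated power for a group random-effect model with cohort (one arm different, r = .30, 33-54 groups) is as follows.

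| Alpha | ICC 0 | ICC .05 | ICC .10 |
|---|---|---|---|
| .05 | 98-99% | 94-98% | 88-95% |
| .008 | 89-94% | 78-88% | 63-84% |

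The joint test without a group term has about 97% at alpha .008 and ICC 0. A team that doubts clustering can still adopt the first step at almost no cost.
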